11.4 Data privacy impact assessment

11.4.1 Systematic description of the envisaged processing operations and the purposes of the processing

The categories of personal data as well as the purposes, scope and duration of the data processing procedures conducted by the sponsor in connection with this clinical trial are described in the attached Clinical Trials Privacy Impact Assessment (see Appendix 4: Clinical Trials Privacy Impact Assessment) which is, inter alia regarding the involved personal data as well as the processing purposes, further specified in this clinical trial protocol.

11.4.2 Assessment of the necessity and proportionality of the processing operations in relation to the purposes

As set out in this clinical trial protocol the processing of personal data performed by the sponsor will only cover personal data being necessary for the performance of the clinical trial. Furthermore, the sponsor will only process the patients' personal data in a pseudonym form. On the other hand the performance of the clinical trial may create new scientific knowledge which may positively affect the health status and medical treatment of the patients. Therefore, the nature and scope of the conducted data processing is necessary, suitable and proportionate in relation to the purpose of the clinical trial.

11.4.3 Assessment of the risks to the rights and freedoms of data subjects

The performance of the clinical trial involves comprehensive processing of sensitive personal data (e. g. data concerning health). Whereas, any unintended and / or unauthorized disclosure of patients data may likely result in a high risk to the rights and freedoms of the patients. Patients may in particular be stigmatized by their social environment, may lose or fail in obtaining insurance coverage. However, the abovementioned risk is significantly reduced by the fact that the sponsor solely obtains and processes pseudonym data which cannot directly be attributed to an individual patient. In order to safeguard that the patient's data stays pseudonym technical and organizational measures have been established to prevent the sponsor from receiving additional information which allows to link the scientific data to individual patients.

11.4.4 Measures envisaged to address the risks, including safeguards, security measures and mechanisms to ensure the protection of personal data and to demonstrate compliance with the GDPR taking into account the rights and legitimate interests of data subjects and other persons concerned.

Confidential

First and foremost, the sponsor exclusively processes pseudonym data which cannot directly be attributed to an individual patient. To safeguard that the personal data processed by the sponsor stays pseudonym technical and organizational measures have been established to avoid that the sponsor obtains additional information which allows the sponsor to attribute pseudonym data to an individual patient. Thus, the described risks for the rights and freedoms of the data subjects are reduced substantially. The sponsor's IT systems being used to process personal data in connection with the clinical trial have thoroughly been assessed from an IT security point of view in order to ensure availability, integrity, confidentiality, and correctness of personal data. The implemented IT security measures in particular reflect the respective sensitivity of the data being processed. To the extent IT systems are operated by external companies on behalf of the sponsor, required data processing agreements have been concluded inter alia stipulating technical and organizational measures to prevent data loss. Furthermore, any personal data is solely disclosed on a need to know basis. The personnel having access to personal data related to the clinical trial undertook to maintain confidentiality or is equally bound by confidentiality and professional secrecy obligations.

12 Data analysis and statistical methods

The statistical analysis will be based on all subject data at the time the trial ends. This analysis will be performed once all patients completed their final visits or terminated the study prematurely.

All analyses will be performed by Novartis or a designated CRO. Any data analysis carried out independently by the investigator should be submitted to Novartis before publication or presentation.

Continuous variables will be summarized by number of patients, mean, standard deviation, minimum, median, and maximum. For selected parameters, 25th and 75th percentiles will also be presented.

Categorical variables will be summarized by frequencies and percentages.

The 95% confidence interval (CI) using the Clopper-Pearson method will be provided for selected parameters. Kaplan-Meier method will be used for time to event analyses.

The **baseline** is the result of an investigation describing the state of the patient before start of eltrombopag or dexamethasone study treatment, and after a possible pre-treatment. The screening value describes the result at screening, before pre-treatment, especially for the thrombocyte count (see exclusion criteria). Should a patient not need pre-treatment, Screening

and baseline values can be identical. In such cases, as only one assessment exists, the baseline value will be taken from screening.

The last available assessment on or before the date of start of eltrombopag / dexamethasone study treatment is taken as "baseline" assessment. In case, assessment is captured pre-dose on first day of study treatment (e.g. PROs), this assessment is used for baseline.

12.1 Analysis sets

The Full Analysis Set (FAS) will consist of all patients to whom study treatment has been assigned by randomization. The FAS will serve as the primary analysis set for all efficacy analyses. According to the intent to treat principle, subjects will be analyzed according to the treatment they have been assigned to during the randomization procedure.

Before database lock, relevant protocol deviations and potential impact on analyses will be reviewed and adequately processed / documented.

The Safety Set (SAF) includes all subjects who received at least one dose of study treatment. Subjects in the SAF will be analyzed according to the study treatment actually received. Further details will be specified in the SAP.

12.2 Subject demographics and other baseline characteristics

Demographic and other baseline data including disease characteristics will be listed and summarized descriptively by treatment group and overall for the FAS.

Relevant medical histories and current medical conditions at baseline will be summarized separately by system organ class and preferred term, by treatment group and overall.

12.3 Treatments

The Safety set will be used for the analyses below.

The duration of exposure in weeks to eltrombopag and dexamethasone as well as the dose intensity (computed as the ratio of actual cumulative dose received and actual duration of exposure) and the relative dose intensity (computed as the ratio of dose intensity and planned dose intensity, and shown separately as well as combined for both drugs) will be summarized by means of descriptive statistics using the safety set.

The number of subjects with dose adjustments (reductions, interruption, or permanent discontinuation) and the respective reasons will be summarized by treatment group and all dosing data will be listed.

Furthermore, subjects using rescue treatments as defined in Section 6.2.3 will be summarized by treatment group.

Concomitant medications and significant non-drug therapies prior to and after the start of the study treatment will be listed and summarized according to the Anatomical Therapeutic Chemical (ATC) classification system, by treatment group.

12.4 Analysis of the primary endpoint

The primary objective is to compare the ability of eltrombopag in combination with a short course of high-dose dexamethasone to induce sustained response off treatment at 52 weeks in newly-diagnosed ITP patients versus 1-3 cycles course of high-dose dexamethasone.

For the primary and supportive analyses the FAS will be used.

12.4.1 Definition of primary endpoint

The primary endpoint is the proportion of patients with sustained response off treatment at 52 weeks.

Sustained response off treatment is defined as:

- reach platelet count $\geq 30 \times 10^9/L$ and then maintain platelet counts $\geq 30 \times 10^9/L$ after treatment discontinuation AND
- maintain platelet count $\geq 30 \times 10^9$ /L in the absence of bleeding events \geq Grade II and without the use of any rescue therapy (see Section 6.2.3) at all visits until week 52.
- Of note: in case a patient in the treatment Arm B (dexamethasone monotherapy) needs treatment cycles at an interval of less than 28 days (at least 14 days), and meets the definition for sustained response off treatment as given above, such patient will be counted as a responder for statistical analysis.

.

12.4.2 Statistical model, hypothesis, and method of analysis

The analysis of the primary endpoint will be based on the following estimand:

The population will be the Full Analysis Set;

Variable of interest: The primary endpoint is the response rate in terms of sustained response off treatment at 52 weeks, in absence of bleeding or use of rescue therapy as defined above, i.e. a composite estimand.

Intervention effect: effect of eltrombopag in combination with a short course of high-dose dexamethasone versus 1-3 cycles of high-dose dexamethasone alone at 52 weeks, regardless of adherence to randomized treatment.

Summary measure: odds ratio

The statistical hypothesis to be rejected is that the rates of patients achieving sustained response at 52 weeks are equal in both treatment groups. The corresponding alternative hypothesis is that the rates are not equal under eltrombopag combined with a short course of high-dose dexamethasone, compared to 1-3 cycles of high-dose dexamethasone monotherapy.

Let p_A and p_B denote the proportions of patients achieving sustained response off treatment for the treatment groups:

A = eltrombopag combined with a short course of high-dose dexamethasone

B = 1-3 cycles of high-dose dexamethasone "standard"

The following hypotheses will be tested:

H₀: $(p_B / (1 - p_B)) / (p_A / (1 - p_A)) = OR_{B/A} = 1$

versus H_A : $(p_B / (1 - p_B)) / (p_A / (1 - p_A)) = OR_{B/A} \neq 1$

In other words:

 H_0 : The rate of patients achieving a sustained response off treatment at 52 weeks in the eltrombopag plus a short course of high-dose dexamethasone arm is equal to the respective rate in the 1-3 cycles high-dose dexamethasone monotherapy "standard" arm (corresponding to equal odds).

 H_A : The rate of patients achieving a sustained response off treatment at 52 weeks in the eltrombopag plus a short course of high-dose dexamethasone arm is higher than the respective rate in the 1-3 cycles of dexamethasone monotherapy "standard" arm.

The primary analysis will be performed comparing the treatment groups with respect to the primary efficacy outcome, based on the Odds Ratio, in a Logistic Regression model with the factor treatment and cofactors ITP-directed pre-therapy (during 3 days within 7 days before randomization), screening platelet count and age ($\leq vs. > 60$ years). The odds ratio and its 95% confidence interval (CI) and p-value will be given. The null hypothesis of equal odds will be rejected if the 2-sided p-value from the logistic regression model for the factor "treatment" is <0.05; however, superiority of eltrombopag in combination with a short course of dexamethasone will be claimed only if the direction is correct, i.e. if the odds of response are higher under eltrombopag plus a short course of high-dose dexamethasone compared to 1-3 cycles of dexamethasone monotherapy (OR_{B/A} < 1).

12.4.3 Handling of missing values/censoring/discontinuations

If patient's platelet assessment for evaluating the primary endpoint are missing, they will not be considered for sustained response off treatment. Patients dropping out early will be considered as early discontinuation or not evaluable, will be considered in the analysis set as non-responders. Thus, missing values are not expected for the primary analysis. Details will be specified in the respective SAP.

12.4.4 Sensitivity and Supportive analyses

Sensitivity analyses

Sensitivity analyses and supportive analyses will be conducted in order to provide evidence that the results seen from the primary analysis are robust. Furthermore, Bayes analyses may be considered in addition (Fisch et al 2015).

The impact of the analysis assumptions on the result of sustained response off treatment will be assessed as well by repeating the logistic regression model using different populations and ways to handle missing data.

These may include, but are not limited to:

- Multiple imputation
- Using a treatment policy estimand (no matter if intercurrent events such as bleeding, treatment discontinuation or reinitiation, or rescue treatment occurred)
- Using the baseline thrombocyte count (or threshold exceedance, i.e. early increase of thrombocyte count above the screening threshold, instead of or in addition to the thrombocyte count at screening),
- Adding further detail information on pre-treatment to the model (type of medication, dosage, duration)

Supportive analyses

Data defining the primary outcome of sustained response off treatment will be further reported descriptively to give the full picture. This will include

- PLT counts at treatment discontinuation
- Number of patients with PLT \ge 50 x 10⁹/L or PLT \ge 100 x 10⁹/L or PLT \ge 150 x 10⁹/L at treatment discontinuation;
- Time point of reaching PLT $\geq 150 \times 10^{9}$ /L measured from start of study treatment
- Number of patients who are able to discontinue eltrombopag and dexamethasone with $PLT \geq 30 \times 10^9 / L$
- Number of patients with loss of response after treatment discontinuation
- Number of patients with bleeding events after treatment discontinuation
- Number of patients receiving rescue treatment

The primary analysis will be repeated in the following subgroups:

- Age (\leq vs. > 60 years).
- Platelet count: thrombocytopenia at screening and at baseline: platelets $<10\times10^9/L$ versus platelets $>10\times10^9/L$
- ITP-directed pre-therapy (yes / no)

12.5 Analysis of secondary endpoints

For all efficacy and PRO analyses, the FAS will be used. For all safety analyses the safety set will be used.

12.5.1 Efficacy endpoints

1. To compare the ability of eltrombopag in combination with a short course of high-dose dexamethasone **to induce overall response (OR)** after treatment discontinuation at week 52 versus a defined course of dexamethasone

Number (%) of patients with platelet count $\ge 30 \times 10^{9}$ /L and a 2-fold increase of screening platelet count after treatment discontinuation in the absence of bleeding events \ge Grade II and no rescue therapy at all visits until Week 52 will be provided, analysis will be equivalent to the primary endpoint analysis.

- 2. To assess the **duration of sustained response off treatment**, median duration of response off treatment (weeks) counted from last dose of study treatment (eltrombopag or dexamethasone) until loss of response will be calculated using a Kaplan-Meier analysis.
- 3. .
- 4. To assess the ability of eltrombopag to induce overall response (OR) by week 4

Number (%) of patients with platelet count $\ge 30 \times 10^9$ /L and a 2-fold increase of screening platelet count at least once within the first 4 weeks without bleeding events \ge Grade II and no rescue therapy will be provided, analysis will be equivalent to the primary endpoint analysis.

- 5. To assess the ability of eltrombopag to induce a **complete response (CR) by week 4** Number (%) of patients with platelet count $\geq 100 \times 10^{9}$ /L at least once within the first 4 weeks without bleeding events \geq Grade II and no rescue therapy will be provided, analysis will be equivalent to the primary endpoint analysis.
- 6. To assess the **platelet count** from screening to baseline and to 1, 2, 4, 12, 26 and 52 weeks; absolute and relative change in platelet count from screening to baseline and to 1, 2, 4, 12, 26 and 52 weeks and EOS will be provided. Box plots for absolute and/or relative change in platelet counts from screening to baseline and to different time points will also be provided.
- 7. To assess the time to response for overall and complete response using a Kaplan-Meier analysis.
- 8. To assess the duration of response for overall and complete response using a Kaplan-Meier analysis.
- 9. To evaluate patient HRQoL outcome measures for Health-Related Quality of Life (fatigue level of the patient through FACIT), FACT-Th6 and SF-36v2 questionnaires. Change in each domain score and total score of HRQoL parameters through FACIT and SF-36v2 questionnaires from baseline to 1, 2, 4, 12, 26, 52 weeks and EOS (for patients with premature study withdrawal before W53D1) will be provided.
- 10. To evaluate the safety and tolerability of eltrombopag see Section 12.5.2.
- 11. To evaluate the incidence and severity of bleeding events

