5.2 Exclusion criteria

Patients meeting any of the following criteria are not eligible for inclusion in this study.

- 1. Previous history of treatment for ITP
 - Note: Patients in need of immediate treatment for thrombocytopenia while diagnosis or eligibility are being determined may receive treatment with any ITP-directed therapy for a maximum of 3 days within 7 days before randomization. These therapies must be discontinued before the patient receives the first dose of study treatment
- 2. Patients with diagnosis of secondary thrombocytopenia
- 3. Patients who have life threatening bleeding complications per physician's discretion
- 4. Patients with a history of thromboembolic events in the 6 months preceding enrollment or known risk factors for thromboembolism (e.g. Factor V Leiden, ATIII deficiency, antiphospholipid syndrome) are excluded. Patients with other risk factors which may pose an increased thromboembolic event (TEE) risk (prolonged periods of immobilization, malignancies, contraceptives and hormone replacement therapy, surgery/trauma, obesity and smoking) would be excluded according to the discretion of the investigator.
- 5. Presence of moderate to severe impaired renal function as indicated by any or all of the following criteria:
 - Creatinine clearance < 45 mL/min as calculated using Cockcroft-Gault formula
 - Serum creatinine > 1.5 mg/dL
- 6. Total bilirubin (TBIL) $> 1.5 \times$ upper limit of normal (ULN)
- 7. Aspartate transaminase (AST) $> 3.0 \times ULN$
- 8. Alanine transaminase (ALT) $> 3.0 \times ULN$

9. Patients who are human immunodeficiency virus (HIV), HCV or hepatitis B surface antigen (HBsAg) positive

Confidential

- 10. Patients with hepatic impairment (Child-Pugh score > 5)
- 11. Patients with known active or uncontrolled infections not responding to appropriate therapy
- 12. History of current diagnosis of cardiac disease or impaired cardiac function denoted by any of the following:
 - Corrected QTc >450 msec using Fridericia correction (QTcF) on the screening electrocardiogram (ECG)
 - History of myocardial infarction and unstable angina within 6 months prior to starting study treatment
 - Clinically significant cardiac arrhythmias or other clinically significant cardiovascular disease (e.g., congestive heart failure, uncontrolled hypertension) within the six months prior to starting study treatment
- 13. Patients who have active malignancy
- 14. Patients with evidence of current alcohol/drug abuse

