#### 1.2 Study objectives and endpoints

Objectives		Endpoints		
4.	To assess the ability of eltrombopag to induce complete response (CR) by Week 4	٠	Proportion of patients with platelet count $\geq 100 \times 10^{9}$ /L and absence of bleeding and no rescue therapy at least once by Week 4	
5.	To quantify the increase in platelet count from baseline to 1, 2, 4, 12, 26, and 52 weeks	•	Absolute values and relative changes in platelet count from screening to 1, 2, 4, 12, 26, and 52 weeks	
6.	To assess the time to overall and complete response	•	Time from starting treatment to time of achievement of overall and complete response	
7.	To assess the duration of overall and complete response		Duration of overall and complete response as defined above	
8.	To evaluate patient-oriented outcomes for health-related quality of life	•	The analysis of Health–Related Quality of Life (HRQoL) parameters by use of Functional Assessment of Chronic Illness Therapy (FACIT) and Short Form 36 version 2 (SF36v2) questionnaires. Change in scores from baseline to 1, 2, 4, 12, 26 and 52 weeks	
9.	To evaluate the safety and tolerability of eltrombopag + dexamethasone	•	Changes from baseline in physical exam findings, clinical monitoring, vital signs, clinical laboratory tests, and evaluation of reported adverse events	
10.	To evaluate the incidence and severity of bleeding events	•	Incidence and severity of bleeding assessed by the World Health Organization (WHO) Bleeding Scale	
		I		

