### 2.1.1 General definitions

**Study treatment** for patients randomized to the investigational combination treatment is eltrombopag until Week 26 in combination with 1 cycle of high-dose dexamethasone (subsequently referred to as treatment group ETB+DEX). For patients randomized to the control arm the study treatment consists of 1-3 cycles of high-dose dexamethasone (subsequently

referred to as treatment group DEX). These treatments will be called "study treatment" in the rest of the document.

When eltrombopag and/or dexame thas one will be given additionally, this is assessed as rescue or - if applicable - as concomitant medication during the data review meeting case-by-case.

The last available assessment on or before the date of start of eltrombopag is taken as "**baseline**" assessment. It is assumed that all assessments at Week 1/Day 1 are captured pre-dose on first day of eltrombopag (e.g. PROs), thus this Week 1/Day 1 is used for baseline when no screening values are available. Otherwise the screening values are considered as baseline. For all analyses on platelets the platelet count directly before pre-treatment will be used as baseline value in the pretreated patients. This is the more adequate way of taking into account the initial value at time of diagnosis and before pre-treatment for all patients

**Pre-treatment period**: from day of subject's informed consent to the day before first dose of study treatment.

**On-treatment period**: from date of first dose of study treatment to date of treatment discontinuation (including start and stop date).

**Treatment discontinuation** is the date of last study medication given as study treatment but not as rescue medication or not after after re-initiation, i.e. initial dose after failure of 1-3 DEX cycles (for details see Derivation of time point of treatment discontinuation5.1).

**Post-treatment period**: starting at day 30+1 after last dose of study treatment

The **Safety Follow-up period** specifies the observational period (30d) for which patients will be followed-up for safety events/measures.

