### 2.7 Analysis of secondary efficacy objective(s)

#### 2.7.1 Secondary endpoints

For all analyses on secondary parameters the FAS is used unless it is specified otherwise.

The following parameters are analysed analogeously to the analysis of primary parameter respectively the supportive analyses on the primary parameter:

- 1) **Overall response** (OR), defined as number (%) of patients with platelet count  $\geq 30 \times 10^9$ /L and a 2-fold increase of screening  platelet count after treatment discontinuation in the absence of bleeding events  $\geq$  Grade II and no rescue therapy at all visits until Week 52 will be provided, analysis will be equivalent to the primary endpoint analysis
- 2) The duration of sustained response off treatment, median duration of response off treatment (weeks) counted from last dose of study treatment (eltrombopag or dexamethasone) until loss of response will be provided calculated using a Kaplan-Meier analysis based on the population
- 3) Overall response (OR) by week 4, presented by number (%) of patients with platelet count  $\ge 30 \times 10^{9}$ /L and a 2-fold increase of screening platelet count at least once

<sup>4 For patients who were pre-treated: the platelet count directly before start of pre-treatment

within the first 4 weeks without bleeding events  $\geq$  Grade II and no rescue therapy will be provided, analysis will be equivalent to the primary endpoint analysis.

- 4) Complete response (CR) by week 4, presented by Number (%) of patients with platelet count  $\geq 100 \times 10^{9}$ /L at least once within the first 4 weeks without bleeding events  $\geq$  Grade II and no rescue therapy will be provided, analysis will be equivalent to the primary endpoint analysis.
- 5) **Platelet count** from screening to 1, 2, 4, 12, 26 and 52 weeks; absolute and relative change in platelet count to screening, 1, 2, 4, 12, 26 and 52 weeks and EOS will be provided. Box plots for absolute and/or relative change in platelet counts from baseline to different time points will also be provided.
- 6) The **time to response for overall and complete response** using a Kaplan-Meier analysis.
- 7) The **duration of response for overall and complete response** using a Kaplan-Meier analysis. Here the following population is used: FAS patients who reached overall respectively complete response.

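### Week 4 response and time to response credit study treatment with platelet criteria that a pre-treated patient may already meet at the Day 1 pre-dose count

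*Protocol*

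**What the plan says.** Protocol 5.2, criterion 1, excludes prior ITP treatment, but patients who need immediate treatment "may receive treatment with any ITP-directed therapy for a maximum of 3 days within 7 days before randomization". Eligibility then rests on the count before that treatment (Protocol 5.1).

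The same count is the reference for response. The introduction to Protocol Section 12 states: "The screening value describes the result at screening, before pre-treatment, especially for the thrombocyte count". The SAP agrees. A footnote in SAP 2.7.1 defines the screening count: "For patients who were pre-treated: the platelet count directly before start of pre-treatment". SAP 2.1.1 adds: "For all analyses on platelets the platelet count directly before pre-treatment will be used as baseline value in the pretreated patients".

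The endpoints concerned are items 4, 5 and 7 of Protocol 12.5.1 (items 3, 4 and 6 of SAP 2.7.1):

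- OR by Week 4: a count of at least 30 × 10⁹/L and "a 2-fold increase of screening platelet count at least once within the first 4 weeks without bleeding events" of Grade II or worse, without rescue.
- CR by Week 4: at least one count of 100 × 10⁹/L or more in the same window, under the same bleeding and rescue conditions. There is no reference count.
- Time to response, in SAP 1.2: "Time from starting treatment to time of achievement of overall and complete response". It is analysed by Kaplan-Meier.

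Protocol 6.2.3 defines rescue within the treatment phase, and separately treats ITP therapy in follow-up as non-response for the primary endpoint. Pre-randomisation therapy therefore does not cancel a response.

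**The concern.** Secondary objectives 3 and 4 ask whether eltrombopag induces response by Week 4, and objective 6 asks how fast response comes. None of the definitions requires the patient to be below the criterion when study treatment starts. Part of the observed early response may therefore come from therapy given before randomisation.

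This is more than a theoretical gap. The Amendment 2 rationale reports patients who were below the platelet threshold at screening and above it at baseline after pre-treatment, and the baseline check was dropped for that reason. The effect was judged negligible for the Week 52 outcome. That argument does not carry over to an endpoint that can be met within days of the pre-treatment.

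The SAP also removes a direct view of the effect. Protocol 12.5.1 item 6 commits to the platelet change from screening to baseline. SAP 1.2 item 5 and SAP 2.7.1 item 5 leave that step out, although SAP Section 4 declares no change from the protocol. Under the SAP 2.1.1 platelet baseline, the step would be zero by definition in every pre-treated patient.

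**Working it through.** **The plan's own figures.** The documents give no figure for the Week 4 or time-to-response endpoints. The one sample-size figure, 47 per arm for 30% versus 65% with 90% power at two-sided 5%, reproduces with a continuity correction (41 without). It rests on the Week 52 endpoint and is not affected here.

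**Step 1: apply the rules to example counts.** The counts (× 10⁹/L) are invented. Bleeding and rescue are assumed absent.

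| Screening | Day 1 | Week 2 | Criterion met on Day 1 | Scored at Week 2 under the plan | Week 2 ÷ Day 1 |
|---|---|---|---|---|---|
| 8 | 45 | 40 | OR (45/8 = 5.6-fold) | OR (40/8 = 5.0-fold) | 0.89 |
| 20 | 70 | 45 | OR (70/20 = 3.5-fold) | OR (45/20 = 2.25-fold) | 0.64 |
| 12 | 110 | 105 | OR and CR | OR and CR (105 ≥ 100) | 0.95 |

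All three met the criterion before the first study dose and fell afterwards, yet all three are scored as responders. None would be an OR responder against the Day 1 count.

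**Step 2: time to response.** If the Day 1 count may itself qualify, the time is zero. If not, it is the first on-study visit, Week 2 Day 1, about 7 days after the start. The documents do not say which applies.

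**Step 3: size per patient.** About 24 patients gives 12 per arm. One patient is 1/12 = 8.3 points. That is the ceiling, reached only if the patient would not otherwise have responded. If such a patient would have responded with probability r, the inflation is (1/12)(1 − r). For r, take the initial response rates that Protocol 4.3 cites for high-dose dexamethasone, as illustration only:

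- OR, r = 82.1%: 8.3 × 0.179 ≈ 1.5 points each; four such patients add (4/12) × 17.9 ≈ 6 points.
- CR, r = 50.5%: 8.3 × 0.495 ≈ 4 points each; four add (4/12) × 49.5 = 16.5 points.
- A chance split of 4 versus 2 between arms shifts the difference by (2/12) × 17.9 ≈ 3 points for OR and (2/12) × 49.5 ≈ 8 points for CR, in either direction.

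**Step 4: effect at arm level.** Let q be the share that already meets the criterion on Day 1 and keeps it to an on-study visit. Then observed rate = q + (1 − q) × r. The documents do not give q; the range below is assumed.

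| q | OR, r = 82.1% | CR, r = 50.5% | A true 20-point difference becomes |
|---|---|---|---|
| 10% | 83.89% | 55.45% | 18 points |
| 30% | 87.47% | 65.35% | 14 points |
| 50% | 91.05% | 75.25% | 10 points |

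The last column is 20 × (1 − q), because the term q cancels when it is equal in both arms.

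**The case against.** The count before pre-treatment is a deliberate choice: Amendment 2 and SAP 2.1.1 argue that it represents the state at diagnosis better. Pre-treatment precedes randomisation, so it is balanced in expectation. The Week 4 models carry pre-therapy as a yes/no cofactor. SAP 2.2.1 displays the primary endpoint and related parameters by pre-therapy, SAP 2.4.2 lists the kind and duration of pre-treatments, and SAP 2.8.3 lists laboratory values by patient and visit, so Day 1 counts will be visible. The Data Review Committee judges OR, CR and their timing (SAP 5.5.4 and 5.5.5) and could handle such cases. After Amendment 3 all results are descriptive.

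Much of this stands. A reader might infer that the comparison is biased towards eltrombopag. The documents do not support that: the systematic effect is dilution, and a chance imbalance can go either way. A reader might also take 8 to 33 points as the inflation from one to four such patients per arm. That is the ceiling, and with the cited response rates the figures are far smaller. Nor does the Amendment 2 text show how many patients were affected, or that any had doubled or reached 100.

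What does not stand is that these safeguards solve the problem. None changes who is counted as a responder. Pre-therapy yes/no does not identify who had already responded, and SAP 2.5.2 lets that cofactor be removed if the model is unstable. It leaves crude rates untouched, and no covariates are specified for the Kaplan-Meier analysis of time to response. The SAP gives no written rule for counts already raised on Day 1. Descriptive reporting also makes the absolute rates and times the main message.

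**Conclusion.** The point holds, as an inexpensive improvement to secondary endpoints. For OR and time to OR the cause is the reference count before pre-treatment. For CR and time to CR it is an absolute threshold with no Day 1 condition; a reader might infer that CR is also measured against the earlier count, but it has no reference count.

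Absolute early-response rates are inflated and times to response shortened. Under the illustrative rates, each affected patient in an arm of 12 adds about 1.5 points to OR and 4 to CR, with a ceiling of 8.3. This assumes that affected patients would otherwise respond at the cited rates, still meet the criterion on study, and have neither a disqualifying bleed nor rescue. The number affected is unknown.

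Two further inferences are not supported. Scoring only counts after the first study dose would not cure this: the patient with 8, 45 and 40 remains a responder. The sensitivity analyses on baseline count and pre-treatment detail in Protocol 12.4.4 are optional and address only the Week 52 outcome, so their absence from the SAP is not evidence on this point. The primary endpoint is not in question here.

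**What to change.** In SAP 2.7.1, items 3, 4 and 6:

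- Keep the planned FAS results.
- Report per arm how many patients already meet the OR platelet criterion, and how many the CR criterion, at the Day 1 pre-dose count.
- Repeat OR by Week 4, CR by Week 4 and time to response in patients who do not already meet the respective criterion on Day 1, shown beside the FAS result. Day 1 status precedes study treatment, so this is a baseline subgroup and not a selection on outcome.

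In SAP 1.2 item 5 and SAP 2.7.1 item 5, restore the platelet change that Protocol 12.5.1 item 6 requires. Label it screening to Day 1 pre-dose, so that the platelet baseline of SAP 2.1.1 does not reduce it to zero in pre-treated patients.

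The cost is SAP wording and a few tables. Protocol Table 8-1 already schedules Day 1 hematology for everyone. The repeat analyses will have a smaller denominator, already small at about 12 per arm, and probably less favourable early-response figures.
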